A real-world study comparing the efficacy of different treatment options for early missed miscarriage.

Funding source: None

Research Institution: Xiangya Third Hospital, Central South University

Research Leader: [name]

Version number: 1.0

Version date: 2023.11.21

A handwritten signature in black ink, appearing to be '[name]' ([name]), the research leader.

Table of contents

Research Proposal Summary	3
Research Text	6
1. Research Background	6
2. Research Objectives	7
3. Research Design	8
4. Research Content	10
5. Key Evaluation Indicators	16
6. Safety considerations	17
7. Statistical Analysis	17
8. Data integrity and quality assurance	18
9. Ethical Statement	18
10. References	18

Research Proposal Summary

Experiment title:

A real-world study comparing the efficacy of different treatment options for early missed miscarriage.

Research objective:

Currently, there is no unified standard for the treatment of missed abortion in clinical practice. This study aims to collect clinical data on this type of disease to compare the differences in efficacy of different treatments. Based on this, it will also explore the synergistic effect of combining different doses of estrogen with medical induction of labor, conduct statistical analysis on the efficacy, and evaluate whether the treatment plan achieves the desired therapeutic effect while reducing the occurrence of complications, thus providing a valid basis for the subsequent clinical treatment of missed abortion.

Experimental Design:

This study is divided into two parts. The first part is a retrospective analysis, which explores the differences in clinical efficacy and reproductive outcomes between surgical and medical treatment for missed abortion. The second part is a prospective study, which explores the impact of different doses of estrogen combined with surgical or medical abortion on the efficacy of early pregnancy missed abortion, and seeks the optimal clinical treatment method for missed abortion .

Experimental procedure:

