① Those with contraindications to medical abortion; ② Those allergic to estrogen or with contraindications to estrogen use; ③ Those unable to follow up according to the follow-up plan; ④ Those with thromboembolic diseases, known or suspected breast cancer, hormone-dependent tumors, etc.; ⑤ Those with vaginal bleeding exceeding the usual menstrual flow; ⑥ Those with serious heart, liver, or kidney diseases; ⑦ Those with serious internal or surgical diseases, malignant

tumors, or mental illnesses who cannot cooperate.

Statistical methods:

using SPSS 26.0 statistical software. Quantitative data were expressed as mean \pm standard deviation, and the independent t-test was used for comparisons between groups. Count data were expressed as percentages (%), and the chi-square test was used for comparisons between groups. The rank-sum test was used for comparisons between groups of ordinal data. $P < 0.05$ was considered statistically significant.

Research Text

1. Research Background

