labor, conduct statistical analysis on the efficacy, and evaluate whether the treatment plan achieves the desired therapeutic effect while reducing the occurrence of complications, thus providing a valid basis for the subsequent clinical treatment of missed abortion.

3. Research Design

Sample size calculation: Retrospective study of 400 cases

A prospective study of 180 cases

flow chart:

4. Research Content

This study is divided into two parts. The first part is a retrospective analysis to explore the differences in efficacy and fertility outcomes among patients with different treatment methods for missed abortion; the second part is a prospective study to explore the impact of different doses of estrogen combined with different treatment methods on the efficacy of treatment for missed abortion in early pregnancy.

Part I retrospective analysis collected data from patients with early pregnancy loss due to miscarriage who visited the Department of Gynecology at Xiangya Third Hospital of Central South University between January 2018 and March 2023. All patients had voluntarily accepted drug or surgical treatment and signed relevant treatment consent forms, and were exempted from signing informed consent forms regarding the data collection.

Part II, a prospective study, collected data from patients with early pregnancy loss due to miscarriage who visited the Department of Gynecology at Xiangya Third Hospital of Central South University between December 2023 and December 2024. All patients received either medication or surgical treatment at their own discretion. All participants were required to provide fully informed consent and sign an informed consent form.

Selection criteria:

① Age 18-40 years ; ② Diagnosed with early pregnancy missed abortion by imaging and laboratory examinations; ③ All indicators of routine examinations before treatment are within the normal range, and there are no serious systemic diseases; ④ No indication for emergency curettage ; ⑤ Good compliance, and follow-up observation as required (prospective study).

Exclusion criteria:

① Those with contraindications to medical abortion; ② Those allergic to estrogen or with contraindications to estrogen use; ③ Those unable to follow up according to the follow-up plan; ④ Those with thromboembolic diseases, known or suspected breast cancer, hormone-dependent tumors, etc.; ⑤ Those with vaginal bleeding exceeding the

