usual menstrual flow; ⑥ Those with serious heart, liver, or kidney diseases; ⑦ Those with serious internal or surgical diseases, malignant tumors, or mental illnesses who cannot cooperate.

4. Research Process

Grouping:

1. Retrospective analysis: Based on the different treatment methods for patients with early missed abortion, patients were divided into a drug treatment group and a surgical treatment group.

2. Prospective study: Patients with early missed abortions were grouped according to their own wishes to choose surgical or medical abortion, and to the use of different doses of estrogen before and after abortion treatment .

This study did not intervene in patient treatment; it only pre-designed and collected relevant data. No additional examinations or tests were performed on patients during the study, and all procedures were conducted according to standard clinical practice. After treatment, patients were divided into surgical and drug treatment groups based on their chosen treatment plans. Furthermore, based on the estrogen dosage chosen by the patients, they were divided into non-stimulatory estrogen, standard-dose estrogen, and high-dose estrogen groups. Data were then statistically analyzed.

Timing of treatment :

The following criteria are considered indicative of missed abortion in early pregnancy: Ultrasound diagnosis of missed abortion includes: ① Crown-rump length $\geq 7\text{mm}$, no fetal heartbeat detected. ② Average diameter of the gestational sac in the uterine cavity $\geq 25\text{mm}$, no embryo detected. ③ No yolk sac seen in the uterine cavity, and no embryo or fetal heartbeat detected after 2 weeks. ④ Yolk sac visible in the uterine cavity, and no fetal heartbeat detected after 11 days.

Treatment methods:

1. Retrospective Analysis: Patients diagnosed with early pregnancy loss at our hospital between January 2018 and March 2023 were included in this study. All patients were

informed of the available treatment options and associated risks before treatment and signed a treatment consent form. Patients were grouped according to their preferred treatment method: medication or surgery.

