(1) Drug treatment group: Patients clinically diagnosed with early pregnancy missed abortion who chose drug treatment were divided into groups according to their own wishes. Patients in the routine group were given mifepristone 50mg twice a day for two consecutive days on the first day, and misoprostol 600µg vaginally or 400µg sublingually on the third day. Patients in the experimental group were given estradiol valerate tablets 2mg twice a day for three days in addition to the treatment given to group A.

① The gestational sac is completely expelled, and the bleeding is less than menstrual flow. There are no contraindications to estrogen use. Patients can choose to take different doses of estrogen after medical abortion based on their own wishes. Group A (the standard group) does not require estrogen supplementation after medical abortion. Group B (the standard group) uses the standard dose of estrogen after medical abortion: 1 day after medical abortion (as above), oral estradiol valerate 1mg twice daily for 21 days, followed by dydrogesterone 10mg for the last 7 days. B i d , starting from day 5 of the next menstrual period, for a total of 2 cycles. Group C was the conventional group, using high-dose estrogen after medical abortion: 1 day after medical abortion (as above), estradiol valerate 2mg was administered orally . B i , 21 days, with dydrogesterone 10mg added for the last 7 days. B i d , starting from day 5 of the next menstrual period, for a total of 2 cycles. Group D (experimental group) did not receive estrogen supplementation after medical abortion. Group E (experimental group) received conventional doses of estrogen after medical abortion: 1 day after medical abortion (as above), estradiol valerate 1mg orally B i d, 21 days, followed by dydrogesterone 10mg for the last 7 days. B i d , starting from day 5 of the next menstrual period, for a total of 2 cycles. Group F was the experimental group, which received high-dose estrogen after medical abortion: 1 day after medical abortion (as above), estradiol valerate 2mg was administered orally . B i , 21 days, with dydrogesterone 10mg added for the last 7 days. B i d , starting from day 5 of the next menstrual period, for a total of 2 cycles. ② If the

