volume of distension fluid in and out; whether there is a decrease in blood oxygen saturation; whether complications such as uterine perforation, acute left heart failure, or gas embolism occur. Postoperative follow-up data : serum β -HCG, complete blood count, CRP, procalcitonin (not necessary), ultrasound to check for retained gestational tract, and if so, record the maximum diameter of the retained tract.

(5) Outpatient follow-up data 3 months after treatment : duration of vaginal bleeding after miscarriage, amount of bleeding, time of menstruation resumption , changes in menstrual flow , whether ultrasound indicates intrauterine adhesions, condition of endometrium, whether intrauterine adhesion surgery was performed, and intrauterine adhesion score.

(6) Pregnancy outcomes: Pregnancy rate after 1 year of trying to conceive (followed up every 6 months) ; spontaneous abortion rate, premature birth rate, full-term birth rate, stillbirth rate in subsequent pregnancies.

Follow-up data is used only for clinical efficacy evaluation.

6. Safety considerations

The data in this study are derived from clinical data and are absolutely safe. The use of estrogen for missed abortion is in accordance with routine clinical treatment, with the standard dose being 2 mg. 4 mg of estrogen is an off-standard dose, but numerous domestic and international studies have shown that high-dose estrogen for women of childbearing age without contraindications to estrogen use can effectively improve patients' clinical symptoms and has a high safety profile.

7. Statistical Analysis

using SPSS 26.0 software. Normally distributed measurement data were expressed as ($\bar{x} \pm s$), and t-tests were used for comparisons between two groups, while ANOVA was used for comparisons among multiple groups. Non- normally distributed measurement data were expressed as the median, and a nonparametric rank-sum test was used . Categorical data were analyzed using the χ^2 test or Fisher 's test. $P < 0.05$ was considered statistically significant.

8. Data integrity and quality assurance

Researchers should ensure that data is authentic, accurate, complete, and traceable, and should ensure the integrity of basic clinical research documents during retention, avoiding intentional or unintentional alteration or loss.

9. Ethical Statement

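### Part II looks for estrogen synergy in 180 women across 12 self-chosen groups, but its stated tests name no interaction or baseline adjustment and leave the contrasts open

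*Protocol*

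**What the plan says.** **Size.** Under Research Design, the entry reads "Sample size calculation: Retrospective study of 400 cases", followed by "A prospective study of 180 cases". No effect, rate, power or dropout is attached to either count.

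**Objective.** The Research objective in the summary, repeated in section 2, is to "explore the synergistic effect of combining different doses of estrogen with medical induction of labor".

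**Groups.** Under Research Process (Grouping), women are "grouped according to their own wishes to choose surgical or medical abortion", and they also choose their estrogen dose. Under Treatment methods, the prospective drug arm has groups A to F, starting with "Group A (the standard group) does not require estrogen supplementation after medical abortion". The surgical arm has groups G to L. The same Grouping text also describes a coarser split into two treatment groups and three estrogen-dose groups.

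**Tests.** The summary says "the independent t-test was used for comparisons between groups", with chi-square and rank-sum tests for other data types. Section 7 says "t-tests were used for comparisons between two groups, while ANOVA was used for comparisons among multiple groups", with rank-sum, chi-square or Fisher tests otherwise, and significance at P<0.05.

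**Outcomes.** Section 5 lists many indicators and marks none as primary.

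**The concern.** Synergy is a statement about an interaction: whether the effect of estrogen depends on what it is combined with. Chi-square, Fisher, rank-sum and t-tests between groups do not estimate one. ANOVA could contain one, but the protocol names it only for comparing several groups.

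Because women choose both treatment and dose, an unadjusted comparison also carries whatever drove that choice. Gestational age, sac size, HCG, parity and earlier uterine procedures are all collected under section 5, but no stated analysis uses them.

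The contrasts are open as well. The text does not say whether the twelve cells or the collapsed groups are compared. Nor does it say where groups D and J belong in the three-dose split, since they take estradiol before the procedure and none after it. At stake is an apparent best regimen that reflects patient choice or a chance result in a small cell, with the stated question unanswered.

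**Working it through.** **1. The plan's own figure.** The documents give no inputs for 180, so it cannot be reproduced. The only efficacy rates are the background figures of 81% (drug) and 96% (surgery). A two-group calculation on them, two-sided 0.05, 90% power, unpooled variance, gives n = (1.960 + 1.282)² × (0.81×0.19 + 0.96×0.04) / 0.15² = 10.51 × 0.1923 / 0.0225 ≈ 90 per group, or 180. Other common settings give totals from about 106 to 320. The protocol does not link these rates to 180, and such a calculation would serve two groups, so the match supports nothing about twelve.

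**2. Layout.** A to F are pre-procedure estradiol (no, yes) × post-procedure dose (none, standard, high). G to L repeat this for surgery. That is 2 × 2 × 3 = 12 cells, and 180/12 = 15 per cell if choices were even (an assumption; no ratio or cap is set).

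**3. Precision of a difference in proportions.** Half-width = 1.96 × √(2 × 0.81 × 0.19 / n), rates assumed near 81%:

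| Comparison | n per group | 95% half-width |
|---|---|---|
| Two single cells | 15 | 28 points |
| Two post-procedure doses, both arms | 60 | 14 points |
| Two halves (treatment, or pre-procedure estradiol) | 90 | 11.5 points |

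**4. Precision of an interaction.** Half-width = 1.96 × √(4 × 0.81 × 0.19 / n). For a continuous outcome, the difference detectable with 80% power is 2.802 × √(4/n) SD. Equal cells are assumed.

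| Interaction | n per cell | Half-width | Detectable | Power at 0.5 SD |
|---|---|---|---|---|
| Treatment × pre-procedure estradiol | 45 | 23 points | 0.84 SD | 39% |
| Treatment × high v no post-procedure dose | 30 | 28 points | 1.02 SD | 28% |
| Pre × post (high v none), drug arm only | 15 | 40 points | 1.45 SD | 16% |

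If both surgical cells sat at 96% instead, the first half-width would be 1.96 × √((2×0.1539 + 2×0.0384)/45) ≈ 18 points. For comparison, main effects at 0.5 SD have 92% power (90 v 90) and 78% (60 v 60). An interaction of 0.5 SD needs 16 × (2.802/0.5)² ≈ 503 women for 80% power.

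**5. Uneven choice.** With splits of 70/30 (treatment), 70/30 (pre) and 40/40/20 (post), the smallest cell is 180 × 0.3 × 0.3 × 0.2 ≈ 3. Power for the first interaction at 0.5 SD falls from 39% to 29%.

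**6. Order of events.** In the drug arm, the A to F choice is described for women whose sac has been completely expelled. Items ② and ③ of the same section allow women with no or partial expulsion 2 mg twice daily outside that scheme. Post-procedure dose therefore comes after expulsion and cannot cause it. Coding the item ② and ③ women as high dose would make failure predict high dose.

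**7. Sparse failures.** At 96% success, 90 surgical women give 90 × 0.04 = 3.6 expected failures.

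**8. Is pre-procedure estradiol one factor?** Groups J and K state 2 mg with no frequency. Group L and the drug experimental group state 2 mg twice daily.

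**The case against.** **The plan does not say it compares all cells.** This stands. A reader might infer pairwise testing of the twelve groups, and could quote 72% for at least one false positive among 66 unadjusted t-tests (simulated, equal null groups). A reader might also quote 8% Fisher power for 81% v 96% at 15 v 15. The documents prescribe neither analysis. ANOVA is named for several groups and is not said to be one-way, and a collapsed grouping is described. The 81% and 96% are drug and surgery rates, for which an even two-group split gives 90 v 90 and 88% Fisher power. Those figures describe what could be done, not what is planned.

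**A factorial model would not settle synergy either.** This largely stands. It makes the interaction estimable, but imprecisely. No arm receives estrogen without an evacuation treatment, so treatment × estradiol shows whether the effect differs between drug and surgery. If synergy means only added benefit with drug treatment, the direct contrast is pre-procedure estradiol within that arm (45 v 45, half-width 1.96 × √(0.3078/45) ≈ 16 points). A two-group test could make that comparison, but the protocol does not fix it and women choose their group.

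**These details belong in an analysis plan, and the aim is only to explore.** This stands in part. Covariate lists and multiplicity rules are often left to such a plan, and none is shown. But the protocol itself selects the tests, they do not fit its stated objective, and an entry headed as a calculation contains none. An exploratory aim lowers the bar for power; it does not remove the need to estimate the quantity named.

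**Conclusion.** The point holds in this form: the stated tests name no interaction, do not adjust for self-selection and leave the contrasts open, so the synergy objective goes unestimated. The 180 has no stated basis. Single-cell comparisons, if made, carry about 28 points either way. The interactions carry about 23, 28 and 40 points. These figures assume equal cells and rates near 81%; uneven choice would widen them, and rates nearer 100% would narrow them.

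Two stronger readings are not supported. The protocol does not commit to testing every pair of cells. A 2 × 2 × 3 model on these data is not an adequately powered test of synergy, and it would be misleading for evacuation if post-procedure dose were included.

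**What to change.** 1. **Primary outcome.** Name complete evacuation without a further procedure. Model it on treatment, pre-procedure estradiol, their interaction and a small set of the baseline variables already listed in section 5. Leave post-procedure dose out. Use a penalised or risk-difference model because surgical failures will be few.
2. **Later outcomes shared by both arms** (bleeding duration, menstrual resumption, adhesions, pregnancy). Add post-procedure dose as an ordered factor and its interaction with treatment, among women eligible for the post-procedure choice. Handle estrogen given outside groups A to F separately. Analyse arm-specific outcomes, such as operation time or time to sac expulsion, within arm.
3. **Reporting.** Present interactions as exploratory, with confidence intervals and the expected precision above. Label the remaining outcomes and any single-cell comparison exploratory too.
4. **Sample size.** Restate the entry as a feasibility number with that precision.
5. **Groups.** Reconcile the pre-procedure estradiol descriptions in J, K, L and the drug experimental group before treating it as one factor.

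The cost is revised wording and a little more analysis work on data already collected. No more women are needed to make the change, but the interaction estimates will be openly imprecise.

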misoprostol is not expelled after medical abortion but there is no heavy vaginal bleeding, continue to administer 400µg of misoprostol sublingually or vaginally 3 hours later . The total daily dose (misoprostol) should not exceed 1800µg . If the misoprostol is still not expelled, surgical treatment may be temporarily withheld on the second day. High-dose estrogen 2mg B id can be combined to improve uterine contraction sensitivity. If the misoprostol is still not expelled, observation for one week or hysteroscopic surgery can be chosen.

③ If part of the pregnancy tissue is expelled without heavy bleeding and vaginal bleeding is less than menstrual flow, surgery may not be necessary initially. For those without contraindications, administer 2mg of estradiol valerate twice daily, check β-HCG weekly, and have a follow-up ultrasound every 2-3 weeks. If, during the waiting period, the pregnancy tissue is expelled and the remaining tissue is less than 5 mm in diameter , an artificial cycle will be initiated . After the next menstrual period, a follow-up ultrasound and HCG test will be performed, and the doctor will assess whether further surgery is needed. If heavy bleeding (more than twice the menstrual flow) occurs during the treatment, emergency hospitalization is required . If infection occurs during the treatment, emergency hospitalization is required, followed by aggressive anti-infection treatment and, depending on the circumstances, a curettage procedure may be necessary.

④ Heavy bleeding during medical abortion, with intensified uterine contractions (such as oxytocin) failing to expel the pregnancy tissue, and excessive bleeding. Examination reveals the pregnancy tissue is still within the uterine cavity, especially with no tissue impaction in the cervical canal (if present, it should be immediately removed with ovum forceps) . If bleeding significantly decreases after ovum forceps clamping , surgery is not performed immediately; instead, uterine contractions are intensified, and β-HCG is checked weekly. A follow-up ultrasound is performed in 3-4 weeks. If vaginal bleeding remains heavier than menstrual flow after clamping, emergency hysteroscopic-assisted or direct hysteroscopic surgery is necessary.

(2) Surgical treatment group: Patients clinically diagnosed with early pregnancy loss and choosing surgical treatment were grouped according to their own wishes. Group G

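### A single three-level estrogen scale, applied after treatment, merges pre- and post-procedure estradiol and allows drug failures to be counted as high-dose

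*Protocol*

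**What the plan says.** Under Research Process, Grouping, the Protocol sorts prospective patients by surgical or medical treatment and according "to the use of different doses of estrogen before and after abortion treatment". The timing is given as "After treatment, patients were divided into surgical and drug treatment groups based on their chosen treatment plans". The estrogen level follows "based on the estrogen dosage chosen by the patients", on one scale of none, standard and high: "they were divided into non-stimulatory estrogen, standard-dose estrogen, and high-dose estrogen groups".

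Treatment methods, item 2, sets out twelve groups. In the drug arm, A to C take no estradiol beforehand. For D to F, "Patients in the experimental group were given estradiol valerate tablets 2mg twice a day for three days". Within each set of three, the dose after abortion is none, 1 mg twice daily or 2 mg twice daily. That choice is described only for women whose sac has been fully expelled and whose bleeding is below menstrual flow. Surgical groups G to L have the same layout. L's pre-procedure dose is 2 mg twice daily, while J and K are given 2 mg with no frequency.

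For drug-treated women without expulsion, the plan adds: "High-dose estrogen 2mg B id can be combined to improve uterine contraction sensitivity". After partial expulsion: "For those without contraindications, administer 2mg of estradiol valerate twice daily". Section 6 fixes the labels, "with the standard dose being 2 mg. 4 mg of estrogen is an off-standard dose".

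**The concern.** The estrogen level is the exposure in every prospective dose comparison, so each woman needs one unambiguous value that does not depend on how her treatment turned out. The scale fails on both counts. It merges two exposures taken at different times and for different purposes. It is applied when the outcome of medical treatment is already known, and the dose it calls high is also one that women may receive because expulsion failed.

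If those women are counted as high-dose, high-dose estrogen looks worse on expulsion than it is. If the level is instead the dose chosen after expulsion, every drug-treated woman with a level is already a success. Neither reading gives a valid comparison of expulsion by dose.

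**Working it through.** The prospective total of 180 is given without inputs, so it cannot be reproduced. Nothing below depends on its justification.

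**Step 1: place the groups on the scale.** Daily estradiol valerate is 1 mg × 2 = 2 mg (standard) or 2 mg × 2 = 4 mg (the off-standard dose in Section 6). Two rules are possible: the highest dose in either phase, or the post-procedure dose alone.

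| Groups | Before (mg/day) | After (mg/day) | Level by highest dose | Level by post-procedure dose |
|---|---|---|---|---|
| A, G | 0 | 0 | none | none |
| B, H | 0 | 2 | standard | standard |
| C, I | 0 | 4 | high | high |
| D | 4 | 0 | high | none |
| E | 4 | 2 | high | standard |
| F, L | 4 | 4 | high | high |
| J | 2 or 4 (unstated) | 0 | standard or high | none |
| K | 2 or 4 (unstated) | 2 | standard or high | standard |

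D, E and J change level under either reading of J's dose. K changes only if its 2 mg is twice daily. The count is therefore three or four of twelve.

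With equal groups (an assumption), 180/12 = 15 per group:
- Highest dose, J and K at 4 mg/day: none 2 × 15 = 30, standard 2 × 15 = 30, high 8 × 15 = 120.
- Highest dose, J and K at 2 mg/day: none 30, standard 4 × 15 = 60, high 6 × 15 = 90.
- Post-procedure dose: 4 × 15 = 60 in each level.

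**Step 2: women with failed or partial expulsion.** They may receive 2 mg twice daily, the daily amount that defines the high post-procedure dose. The Protocol does not say whether they keep a level, move to high or are left out. Because the post-procedure choice is described only after complete expulsion, they have no post-procedure level of their own to keep.

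**Step 3: effect of relabelling with no true dose effect.** Inputs: 81% success with drug treatment (Protocol, Section 1); 90 drug-treated women, 30 per level (assumed); a share r of the failures in the none and standard levels relabelled as high (assumed). Each level has 30 × 0.81 = 24.3 successes and 5.7 failures.

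- Success in none or standard = 24.3 / (30 − 5.7r)
- Success in high = 24.3 / (30 + 2 × 5.7r)

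| r | None or standard | High |
|---|---|---|
| 0 | 24.3/30 = 81% | 24.3/30 = 81% |
| 0.25 | 24.3/28.575 = 85% | 24.3/32.85 = 74% |
| 0.50 | 24.3/27.15 = 90% | 24.3/35.7 = 68% |
| 1 | 24.3/24.3 = 100% | 24.3/41.4 = 59% |

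The percentages are the same for 60 or 120 drug-treated women, because the level size cancels. In 20,000 simulations of the three-group chi-square test at 0.05 with 30 women per level, the false-positive rate was 4.7% at r = 0, 18% at r = 0.25 and 60% at r = 0.50.

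**Step 4: the dose contrast before expulsion.** In the drug arm, pre-procedure estradiol is either 0 or 4 mg/day. The contrast between 2 and 4 mg/day begins the day after abortion. The objective of combining different doses with medical induction (Section 2) can therefore be met, as a comparison of doses, only for outcomes after expulsion.

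**The case against.** The best defence is that groups A to L already form the right two-way structure, and that the three levels simply summarise the post-procedure dose. On that reading every group has exactly one level and one clarifying sentence would suffice. The flow chart is not shown and may depict this, and the handling of rescue medication is often left to the SAP. Part of this stands: the two-way layout exists and needs no redesign. But the Grouping text itself names use both before and after treatment. The post-procedure reading also leaves the drug-arm levels made up of women who have already expelled the sac, so expulsion still cannot be compared across them.

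Several stronger readings are tempting, and the documents do not support them:
- A reader might infer that the Protocol moves rescued women into the high-dose group. It does not say so. It speaks of the dose the patient chose, and the estradiol is optional after non-expulsion and limited after partial expulsion to women without contraindications. Relabelling is possible, not prescribed.
- A reader might take 41% against 0% failures (17.1/41.4 against 0/24.3) as the expected distortion. It requires every failure in the lower levels to be relabelled and is only an upper bound. The plan names no estrogen for the heavy-bleeding pathway.
- A reader might infer that leaving out the rescued women would make high-dose look helpful. If the levels then hold only successes, all three show 0% failure and no benefit appears.
- A reader might say there is no estrogen contrast at all before expulsion. There is one, none against 2 mg twice daily. What is missing is a contrast between doses.

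**Conclusion.** The point holds. As written, the single scale cannot validly compare expulsion by estrogen dose, because the level is either set after success or open to contamination by estradiol given for failure. Three groups have no unique level, or four if K's pre-procedure dose is twice daily. The distortion depends on the share of failures relabelled, which the documents do not give. A quarter to a half would produce apparent success differences of about 11 to 21 percentage points where none exists. This rests on the Protocol's 81%, on equal levels and on no true effect. Equal group sizes are unlikely to hold exactly when patients choose, so the head counts are illustrative, but the ambiguity does not depend on them.

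**What to change.** Replace the three-level grouping in Research Process by two variables, each fixed at its decision point: pre-procedure estradiol (no or yes) when treatment starts, and post-procedure dose (none, standard, high) when that choice is made. Then:

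- Compare initial expulsion and need for surgery by pre-procedure estradiol in all drug-treated women, failures included.
- Compare post-procedure doses only among women eligible for that choice (in the drug arm, those with complete expulsion), and only for outcomes arising afterwards: bleeding, menstruation, adhesions and later retained tissue.
- Record estradiol given after failed or partial expulsion as a post-baseline event that does not change the woman's group.
- Restate the dose objective to match.
- Reconcile the pre-procedure wording for J and K with that for L.

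The cost is Protocol and analysis wording. Section 5, item (3), already records drug type, dosage and time of expulsion for drug treatment. The price in scope is that the post-procedure dose comparison no longer speaks to expulsion and excludes drug failures. No change to clinical care is proposed.
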